study reported seven implant fixtures (13.0%) displaying mid facial recession of <0.5mm at 12 months, and 29 patients (53.7%) exhibiting a vertical gain of keratinized soft-tissue from baseline to 12 months. No implant sites demonstrated recession of >0.5mm at 12 months. Thus, a statistically significant gain in keratinized soft tissue on the mid-facial aspect of the experimental abutments with inwardly narrowed profiles at the transmucosal level was observed. The authors attributed the gain in keratinized soft tissue height to three principle factors afforded by the abutment's concave secondary plane:

1. The circumferential concavity created a profile that enabled a localized thickening of the soft-tissues to occur, relative to a divergent abutment.
2. The curved concave profile allowed for an increase in length of the soft tissue-to-abutment interface, meaning that a greater biological seal could be obtained for the same vertical height of the implant platform relative to the gingival margin.
3. The circumferential concavity enabled a greater amount of connective tissue attachment to form, enabling a more robust seal to be established.

In a 2009 study, Redemagni et. al (8) examined 28 patients treated with 33 XiVE implant fixtures restored with concave facial emergence profile abutments in the anterior maxillary region for a mean of 20.4 months. For this study population, a mean of 0.0mm (range of -0.5mm to +1.0mm) of labial mucosal recession was observed. The authors' observations agreed with Rompen's findings that concave facial emergence designs were consistent with facial soft tissue stability, most likely due to increased connective tissue volume in the apical transition zone.

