The investigators propose to utilize a standardized digital stereotactic photography setup (Canfield Dental Camera, Canfield Imaging Systems, Fairfield, NJ) (Fig. 3) from the date of abutment/restoration delivery, and subsequently at 1, 3, 6, and 12 months to accurately document the dynamics of the facial soft tissue. Use of standardized stereotactic digital photography will enable greater accuracy and precision with regard to soft-tissue zenith measurements over time (Fig. 4). This technique is currently being employed as part of a Dentsply Implants-sponsored prospective, randomized, multicenter study called “PROOF” (YA-OSS-0003). After photographic documentation is completed for all time points, a digital software analysis program such as NIH Image J (National Institutes of Health, Bethesda, MD) can be utilized to measure length changes at the mid-facial gingival crest to any desired scale (i.e., tenths of a millimeter or pixels). At recall visits, bucco-lingual peri-implant mucosal thickness will be measured from a fixed reference point, as well as other clinical parameters that include: Plaque Index (PI), Gingival Index (GI) (10), probing pocket depth (PPD), bleeding on probing (BOP) and keratinized mucosa width (KMW) using a UNC-style probe (Fig. 6). These data will be used along with the photographic data to extrapolate the potential role that concavities in the abutment transition zone may play in preserving or enhancing facial soft tissue dynamics.

FIGURES:

[figure not shown]

Fig 6a Mesiodistal section of FM group implant.

Fig 6b Mesiodistal section of CMG group implant.

Fig 6c Mesiodistal section of SA group implant.

(Fig. 1) Histological sections of FM (Fig. 6a), CMG (Fig. 6b), and SA (Fig. 6c) transmucosal profiles, demonstrating superior quantity of connective tissue for CMG configurations.

(Fig. 2) Proposed configurations of the submucosal transition zones of either linear divergent (left) or concave (right) Atlantis™ abutments. Relative lengths of either the divergent (Ld) or concave (Lc) can be calculated

[figure not shown]
during the design/manufacturing process. The volumetric space (x) provided for by the experimental concavity can also be extrapolated from the Atlantis™ software.

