### Average Keratinized Mucosa Width

### Statistical Analyses

We used mixed models to analyze the effect of time and treatment on each of the variables of interest. The results are summarized in tables below.

Canfield values, bleeding on probing, plaque index, gingival index, and keratinized mucosa width changed significantly over time. Canfield values, bleeding on probing, plaque index, and keratinized mucosa width have a curved relationship with time. Treatment alone is not significant in any model, but is significant in

an interaction with time in bucco-lingual thickness; the effect of treatment on this measure is significantly different across time points.

Table 13: Canfield Model

	P-Value
Time	< .001
Time 	< .001
Treatment	0.853

Table 14: Probing Depth Model

	P-Value
Time	0.096
Treatment	0.307

Table 15: Bleeding on Probing Model

	P-Value
Time	0.0791
Time 	0.0282
Treatment	0.9170

Table 16: Plaque Index Model

	P-Value
Time	0.1640
Time 	0.0436
Treatment	0.9880

Table 17: Gingival Index Model

	P-Value
Time	0.00146
Treatment	0.40900

Table 18: Bucco-Lingual Thickness Model

	P-Value
Time	0.0744
Time 	0.1440
Treatment	0.6740
Treatment:Time	0.0169
Treatment:Time 	0.0359

Table 19: Keratinized Mucosa Width Model

	P-Value
Time	< .001
Time 	< .001
Treatment	0.106

Over time, there was not a significant relationship between bucco-lingual thickness and any of Canfield values, probing depth, bleeding on probing, or keratinized mucosa.

Table 20: Canfield and Bucco-Lingual Thickness

	P-Value
Time	< .001
Time 	< .001
Thickness	0.178

Table 21: Probing Depth and Bucco-Lingual Thickness

	P-Value
Time	0.0928
Thickness	0.6720

Table 22: Bleeding on Probing and Bucco-Lingual Thickness

	P-Value
Time	0.1190
Time 	0.0381
Thickness	0.7340

Table 23: Keratinized Mucosa Width and Bucco-Lingual Thickness

	P-Value
Time	< .001
Time 	< .001
Thickness	0.705

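### The zenith model behind the 'no thickness relationship' sentence (Table 20) is over 99% within-subject, so it does not test whether sites with thicker mucosa keep their margin better

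*Combined protocol and SAP*

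**What the plan says.** The first Statistical Analyses section of the statistical report states: "Over time, there was not a significant relationship between bucco-lingual thickness and any of Canfield values, probing depth, bleeding on probing, or keratinized mucosa". The four models behind it are Tables 20 to 23. The zenith model, "Table 20: Canfield and Bucco-Lingual Thickness", lists Time, Time squared and one thickness row ("Thickness 0.178"). The rows for probing depth ("Thickness 0.6720"), bleeding ("Thickness 0.7340") and keratinized width ("Thickness 0.705") have the same form. No table shows a treatment row, a subject-mean row, an estimate, a standard error or an interval.

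The protocol gives thickness a role in the argument. Materials and method lists, as the first explanation for margin stability in a cited pilot study, that the concave profile allowed "a localized thickening of the soft-tissues to occur, relative to a divergent abutment". It also says the clinical measurements, thickness included, will be used with the photographs to "extrapolate the potential role that concavities in the abutment transition zone may play in preserving or enhancing facial soft tissue dynamics". Statistical methods makes subject a random effect and allows for a time-dependent covariate, but describes no separation of within- and between-subject effects. The Baseline-adjusted Analysis section never relates thickness to change in the zenith.

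**The concern.** When a covariate varies both between subjects and within a subject over time, a single slope in a random-intercept model averages two different associations. One is whether a subject's zenith moves when that subject's thickness reading moves. The other is whether subjects with thicker mucosa differ from subjects with thinner mucosa. Each is weighted by its precision. Zenith levels differ widely between subjects and move little within a subject, so the random intercept absorbs nearly all the between-subject information.

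The clinically interesting question is the second: do thicker sites keep their margin? A reader who takes the sentence as evidence against that idea would be relying on a coefficient that hardly bears on it.

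**Working it through.** **Stated figures.** The Table 20-23 p-values need subject-level data and cannot be reproduced. The summary tables are coherent: 12-month zenith change from Table 1 is 9.596 − 9.770 = −0.174 (concave) and 9.622 − 9.860 = −0.238 (divergent), as in Table 24.

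**Assumptions.** Random subject intercept (the protocol's structure; the report says only mixed models), thickness entered as the reading at each visit, m = 5 visits, N = 29 + 25.

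**Thickness variation (Table 11).** The mean of the five visit variances is 0.5167 (concave) and 0.6342 (divergent). The variance of the subject average is 0.4731² = 0.2238 and 0.5159² = 0.2662.
- Within-subject sum of squares: 29×5×(0.5167 − 0.2238) + 25×5×(0.6342 − 0.2662) = 88.5.
- Between-subject: 29×5×0.2238 + 25×5×0.2662 = 65.7.

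**Zenith variation (Tables 1 and 24).** The mean total variance is 1.393. The pooled SD of change is 0.289 mm. Residual variance = 0.289²/2 = 0.0417; between-subject variance = 1.393 − 0.0417 = 1.351 (intraclass correlation, ICC, 0.970).

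**Weights.**
- Within: 88.5/0.0417 ≈ 2,120, SE of slope about 0.022 mm per mm.
- Between: 65.7/(0.0417 + 5×1.351) ≈ 9.7, SE about 0.32 mm per mm.
- Within share: 2,120/(2,120 + 9.7) = 99.5%. Over the printed change SDs (0.362 down to 0.180) it runs from 99.3% to 99.8%. Without the delivery visit it is 99.0%.

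**Simulation check** (80 REML fits per setting, 54 subjects, five visits, between-subject SD 1.15, residual SD 0.2). With a true between-subject slope of 1.0 and a within slope of 0, the single term averaged 0.005 and was significant in 4% of runs. The split model recovered 0.95, significant in 83%.

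**Other outcomes.** With residual variance 1 − ICC and between-subject variance ICC:
- Keratinized width (five visits, N = 31 + 27, sums of squares 95.1 within and 70.6 between). At ICC 0.7: 95.1/0.3 = 317 against 70.6/3.8 = 18.6, so 94%. At 0.9: 98%. The change SDs in Table 26 put the divergent arm slightly lower, near 0.67; at 0.6 the share is 92%.
- Probing depth and bleeding (four recalls, sums of squares 40.6 and 51.1). No change or subject-average SDs allow an ICC to be derived. Within share is 44% at ICC 0, 61% at 0.2, 80% at 0.5 and 93% at 0.8.

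**Stability of thickness.** Covariance of delivery with a recall = (delivery variance + recall variance − change variance)/2, from Tables 11 and 25. The correlations are −0.03 to 0.42 (concave) and 0.15 to 0.46 (divergent). Removing these covariances from the variance of the subject average leaves a mean recall-recall covariance of 0.159 (concave) and 0.166 (divergent). Divided by mean recall variances of 0.327 and 0.474, that gives about 0.49 and 0.35. The delivery reading supplies about 65% (concave) and 50% (divergent) of the within-subject variation.

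**Precision of a subject-level analysis.** The pooled SD of 12-month zenith change is 0.32 mm and the SD of mean recall thickness is about 0.47 mm. SE = 0.32/(0.47×√54) = 0.093 mm per mm. For 80% power the observed slope must be about 2.80×0.093 = 0.26. A four-recall mean has reliability 4r/(1 + 3r) = 0.68 at r = 0.35 and 0.79 at r = 0.49, so the true slope would need to be about 0.26/0.79 = 0.33 to 0.26/0.68 = 0.38.

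**The case against.** The report's sentence is qualified as being over time and says not significant, not unrelated. Read as a within-subject statement, it describes Table 20 fairly. On the assumptions above, p = 0.178 implies a slope of about 0.03 mm per mm in size, with a 95% half-width of about 0.04. A time-dependent covariate was foreseen, and no objective or planned analysis names a thickness-zenith association. All of this stands, and it makes the matter supplementary. But the report does not say which association it examined.

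Four stronger readings are tempting and are not supported:
- **That the subject-level question is untested for all four outcomes.** The 99% belongs to the zenith. For probing depth and bleeding the coefficient may carry a sizeable between-subject part, so there the question is blended rather than untested.
- **That thickness is just a noisy reading.** Low correlations across visits fit measurement error or real tissue change after delivery, and no repeatability is reported.
- **That unreliability merely shrinks the Table 20 slope to 20-50% of its true value.** That rule belongs to a cross-sectional regression. If thickness is a stable site feature, the within slope is zero and the coefficient falls below 1% of the subject-level slope.
- **That these models are the only test of the proposed mechanism.** The arm comparisons of thickness (Tables 18 and 28) address the first link directly, and those of the zenith (Tables 13 and 27) the end result.

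**Conclusion.** The point holds for the zenith. Given a random intercept and a visit-level thickness term, both inferred because the report prints neither, over 99% of the Table 20 coefficient is within-subject. If thickness is a stable site feature, that coefficient would be near zero whatever the subject-level slope. Even its small between-subject part concerns the absolute zenith level, not margin loss. Keratinized width is mostly within-subject; probing depth and bleeding are an unknown mixture that depends on an ICC the documents do not give.

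None of this shows that thickness does relate to margin stability. It limits what the sentence can support. The randomized comparisons, including the primary outcome, are untouched.

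**What to change.** In Tables 20-23 replace the thickness term with two: the subject's mean recall thickness and the visit's deviation from it. Add arm. For the zenith, use change from delivery as the outcome; on absolute levels the between-subject SE would be about 0.32 mm per mm and differences in crown height would be mixed in. Report both slopes with 95% intervals, state the random-effects structure, and reword the conclusion to say which association, within or between subjects, was examined. If the models are not refitted, at least limit the zenith statement to within-subject association and say that the other models do not separate the two.

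The cost is two derived variables, four refits on existing data, and one or two more parameters per model. With a detectable true slope of about 0.33 to 0.38 mm per mm, against mean 12-month changes of only −0.17 to −0.24 mm, the refit may well return another null. The interval would then show how much it rules out.

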### Baseline-adjusted Analysis

We adjusted for baseline values of Canfield, bucco-lingual thickness, and keratinized mucosa width by subtracting the baseline from each subsequent measure, since any differences at delivery for these variables should be due to chance and not implant type.

Table 24: Canfield (Adjusted for Baseline)

Treatment	Mean	SD	Min	Max	Median	N
1 Month						
Concave	-0.152	0.180	-0.74	0.09	-0.15	29
Divergent	-0.176	0.302	-0.73	0.73	-0.14	25
3 Month						
Concave	-0.160	0.242	-0.89	0.54	-0.15	29
Divergent	-0.185	0.329	-0.91	0.71	-0.17	25
6 Month						
Concave	-0.171	0.280	-0.99	0.54	-0.15	29
Divergent	-0.207	0.323	-0.74	0.72	-0.23	25
12 Month						
Concave	-0.174	0.278	-0.84	0.54	-0.20	29
Divergent	-0.238	0.362	-0.85	0.75	-0.31	25

Average Canfield (Adjusted for Baseline)

[figure not shown]

Table 25: Bucco-Lingual Thickness (Adjusted for Baseline)

Treatment	Mean	SD	Min	Max	Median	N
1 Month						
Concave	-0.218	1.138	-3.5	2.0	0.0	31
Divergent	-0.056	1.204	-3.5	2.0	0.0	27
3 Months						
Concave	-0.347	1.030	-3.0	1.5	0.0	31
Divergent	0.120	1.244	-2.5	3.0	0.0	25
6 Months						
Concave	-0.258	1.175	-4.0	2.0	0.0	30
Divergent	0.200	1.199	-3.5	2.0	0.5	25
12 Months						
Concave	-0.267	1.250	-3.5	2.0	0.0	29
Divergent	0.020	1.036	-2.0	2.5	0.0	25

Average Bucco-Lingual Thickness (Adjusted for Baseline)

[figure not shown]
[figure not shown]

Table 26: Keratinized Mucosa Width (Adjusted for Baseline)

Treatment	Mean	SD	Min	Max	Median	N
1 Month						
Concave	0.629	1.056	-1	4.0	0.5	31
Divergent	0.704	0.737	0	2.0	0.5	27
3 Months						
Concave	0.871	1.162	-2	4.0	1.0	31
Divergent	0.800	0.890	-1	2.5	1.0	25
6 Months						
Concave	0.717	1.031	-1	4.0	0.5	30
Divergent	0.658	0.863	-1	2.0	0.5	25
12 Months						
Concave	0.672	1.144	-3	4.0	1.0	29
Divergent	0.740	0.914	-1	2.0	1.0	25

Average Keratinized Mucosa Width (Adjusted for Baseline)

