### Study objectives

- (Primary) Compare the influence of experimental concavities in the subgingival transition zone of Atlantis™ abutments on peri-implant mucosal dynamics from final restoration delivery to one year, as compared to current Atlantis™ abutments with linear divergent transition profiles.
- (Secondary) Quantify the horizontal soft tissue thickness changes around concave and divergent abutment transition profiles from final restoration delivery to one year.
- (Secondary) Evaluate changes in peri-implant health indicators, such as Gingival Index (GI), Probing Pocket Depth (PPD), and Bleeding on Probing (BOP).

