A unified repeated measures analysis (11,12) will be used to describe the time course and to assess the effects of divergent vs. concave abutment design. This approach will make it possible to take into account the correlation of repeated measures on a given subject over time, and to consider the impact of abutment type, as well as other potential covariates. Subject will be treated as a random effect and other factors as fixed effects. Candidate covariate effects that will be explored include sex, age, history of periodontal disease, tooth position, clinical crown anatomy and the condition of adjacent teeth. So as not to exceed the limitations of sample size, we will first consider the relationship of each candidate with the outcome separately, and incorporate those with promising relationships into subsequent modeling. Parameters will be estimated using restricted maximum likelihood

(REML) methods, and a variety of different variance-covariance structures will be entertained, as appropriate. These approaches can accommodate missing data and possible time-dependency of the covariate, both of which may be relevant to this situation. Appropriateness of assumptions associated with the modeling, such as normality, will be fully assessed, and normalizing transformations considered as appropriate. Should these approaches not appear feasible, nonparametric methods for longitudinal data (13, 14) will be considered.

Comparisons of tissue alterations between the two abutments types at each follow-up time are also of interest: Changes relative to baseline will be compared at each of the four recall time points, initially using either the two-sample Student's t-test to compare abutment types, or its nonparametric analog, the Wilcoxon rank sum test, as appropriate. In addition, standard linear modeling will be used to incorporate the possible impact of other covariates. Adjustment for multiple comparisons will be made using the modified Bonferroni method due to Holm (15) in conjunction with an overall Type I error of 0.05.

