### Average Plaque Index

### Average Gingival Index

[figure not shown]

Table 11: Bucco-Lingual Thickness

Treatment	Mean	SD	Min	Max	Median	N
Baseline						
Concave	2.814	1.1291	1.0	6.0	2.50	31
Divergent	2.722	1.1294	1.0	6.0	2.50	27
1 Month						
Concave	2.597	0.6248	1.0	4.0	2.50	31
Divergent	2.667	0.6202	1.5	4.0	2.50	27
3 Months						
Concave	2.468	0.5764	1.5	3.5	2.50	31
Divergent	2.840	0.7176	1.5	4.0	3.00	25
6 Months						
Concave	2.517	0.5796	1.5	3.5	2.50	30
Divergent	2.920	0.6403	1.5	4.5	3.00	25
12 Months						
Concave	2.500	0.5000	2.0	4.0	2.50	29
Divergent	2.740	0.7654	1.5	4.0	3.00	25
Average						
Concave	2.594	0.4731	1.9	3.7	2.55	31
Divergent	2.785	0.5159	1.8	3.7	2.80	27

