### Statistical Analyses

We used mixed models to analyze the effect of time and treatment on each of the variables of interest. The results are summarized in tables below.

For Canfield, time was marginally significant but treatment was not. For bucco-lingual thickness, there were significant interactions between treatment and both time and time: the effect of treatment changed over time. In the keratinized mucosa model, neither time nor treatment were significant.

Table 27: Canfield Model (Adjusted for Baseline)

	P-Value
Time	0.0571
Treatment	0.6130

Table 28: Bucco-Lingual Thickness Model (Adjusted for Baseline)

	P-Value
Time	0.5680
Time 	0.5760
Treatment	0.8330
Treatment:Time	0.0465
Treatment:Time 	0.0510

Table 29: Keratinized Mucosa Width Model (Adjusted for Baseline)

	P-Value
Time	0.694
Treatment	0.952

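### Bucco-lingual thickness: subtracting the delivery value gives visit-level arm contrasts about 3.2 to 3.9 times the variance of covariate adjustment (lost precision, not bias)

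*Combined protocol and SAP*

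**What the plan says.** The first-listed secondary objective of the protocol is to "Quantify the horizontal soft tissue thickness changes around concave and divergent abutment transition profiles", from delivery of the restoration to one year. For the primary outcome, the protocol's Statistical methods section states: "Changes relative to baseline will be compared at each of the four recall time points". It applies Holm adjustment at an overall 0.05 and extends the approach to the quantitative secondary outcomes. It adds that "standard linear modeling will be used to incorporate the possible impact of other covariates", but the delivery value is not among the candidate covariates it lists.

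The statistical report of October 2019 handles baseline by subtraction: "We adjusted for baseline values of Canfield, bucco-lingual thickness, and keratinized mucosa width by subtracting the baseline from each subsequent measure". Its reasoning is that differences at delivery can only be chance. Raw thickness is in "Table 11: Bucco-Lingual Thickness" and changes are in "Table 25: Bucco-Lingual Thickness (Adjusted for Baseline)". Two mixed models follow: "Table 18: Bucco-Lingual Thickness Model" on unsubtracted values and "Table 28: Bucco-Lingual Thickness Model (Adjusted for Baseline)" on changes. Both give p-values only. Neither model table has a row for delivery thickness as a covariate, and no thickness difference between arms with a confidence interval is given at any visit.

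**The concern.** Subtraction fixes the slope of the follow-up value on the delivery value at 1. That is efficient when the two are strongly correlated and have similar spread. Here delivery thickness is far more variable than any later measurement, and the correlation is weak. Subtracting it therefore adds noise to every follow-up value. In every arm and at every visit, the change SD in Table 25 exceeds the raw SD in Table 11.

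Because the report gives no arm differences for thickness, a reader who wants the planned visit comparisons has to build them. Table 25, the table described as baseline-adjusted, is the natural source. Intervals built from it are much wider than the data support, for an outcome the protocol set out to quantify.

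**Working it through.** **Inputs** (mm; SD, with n in brackets). Delivery, Table 11: concave mean 2.814, SD 1.1291 (31); divergent mean 2.722, SD 1.1294 (27).

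| Visit | Concave: follow-up SD / change SD (n) | Divergent: follow-up SD / change SD (n) |
|---|---|---|
| 1 month | 0.6248 / 1.138 (31) | 0.6202 / 1.204 (27) |
| 3 months | 0.5764 / 1.030 (31) | 0.7176 / 1.244 (25) |
| 6 months | 0.5796 / 1.175 (30) | 0.6403 / 1.199 (25) |
| 12 months | 0.5000 / 1.250 (29) | 0.7654 / 1.036 (25) |

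**Do the two tables agree?** The documents give no precision figure for this analysis to reproduce, but the mean changes can be checked wherever nobody is missing. Concave at 1 month: 2.597 - 2.814 = -0.217 (table: -0.218). Concave at 3 months: 2.468 - 2.814 = -0.346 (-0.347). Divergent at 1 month: 2.667 - 2.722 = -0.055 (-0.056). They agree to rounding.

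**Step 1, covariance.** From the variance of a difference, cov = (SD_delivery² + SD_follow-up² - SD_change²)/2. At 1 month:
- concave: (1.2749 + 0.3904 - 1.2950)/2 = 0.1851
- divergent: (1.2755 + 0.3846 - 1.4496)/2 = 0.1053

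**Step 2, pool within arms with weights n - 1.** At 1 month:
- S_xx (delivery) = 71.41, S_yy (follow-up) = 21.71, S_xy = 8.29, S_dd (change) = 76.54
- common slope b = S_xy/S_xx = 8.29/71.41 = 0.116
- change variance = 76.54/56 = 1.367
- covariate-adjusted residual variance = (21.71 - 8.29²/71.41)/55 = 0.377

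**Step 3, standard errors.** With h = 1/31 + 1/27 = 0.0693 and a delivery difference between arms of 0.092:
- change score: √(1.367 × 0.0693) = 0.308
- covariate-adjusted: √(0.377 × (0.0693 + 0.092²/71.41)) = 0.162
- variance ratio: (0.308/0.162)² = 3.6

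**All visits**, concave minus divergent:

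| | 1 month | 3 months | 6 months | 12 months |
|---|---|---|---|---|
| Pooled correlation | 0.21 | 0.28 | 0.17 | 0.24 |
| Pooled slope | 0.12 | 0.16 | 0.09 | 0.13 |
| Change score (95% CI) | -0.16 (-0.78 to 0.45) | -0.47 (-1.08 to 0.14) | -0.46 (-1.10 to 0.19) | -0.29 (-0.92 to 0.35) |
| Covariate-adjusted (95% CI) | -0.08 (-0.40 to 0.24) | -0.39 (-0.72 to -0.05) | -0.41 (-0.74 to -0.08) | -0.25 (-0.59 to 0.10) |
| SE, change score | 0.308 | 0.304 | 0.321 | 0.316 |
| SE, covariate-adjusted | 0.162 | 0.167 | 0.164 | 0.170 |
| SE, raw follow-up | 0.164 | 0.173 | 0.165 | 0.174 |
| Variance ratio, change / adjusted | 3.62 | 3.29 | 3.85 | 3.43 |
| Variance ratio, change / raw | 3.5 | 3.1 | 3.8 | 3.3 |
| Holm p, change score | 0.73 | 0.52 | 0.52 | 0.73 |
| Holm p, covariate-adjusted | 0.62 | 0.074 | 0.064 | 0.31 |

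**Attrition.** The 1-month ratio needs no assumption, because all subjects are present. For later visits the delivery SD of those remaining is not printed, but follow-up mean minus change mean gives their delivery mean. The missing delivery values therefore sum to 5.5 (two divergent subjects from 3 months), 4.0 (one concave at 6 months) and 7.0 (two concave at 12 months). Trying splits in 0.25 mm steps within the tabled range of 1.0 to 6.0 gives delivery SDs of 1.06 to 1.18 (divergent), 1.13 (concave, 6 months) and 0.94 to 1.15 (concave, 12 months). The equal-variance, common-slope ratios become 3.22 to 3.35, 3.79 to 3.89 and 3.24 to 3.52, and the smallest Holm p becomes 0.060 to 0.068.

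**Separate slopes.** At 12 months the implied slopes differ by arm: -0.01 concave and 0.31 divergent. With a separate slope per arm the ratios are 3.6, 3.2, 3.7 and 3.4, and the smallest Holm p is 0.072.

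**Other outcomes.** The same calculation gives a ratio of about 1.0 for Canfield and 1.1 to 1.3 for keratinized mucosa width.

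**Interaction terms in Table 28.** The subtracted value is constant within a subject, so a subject effect absorbs most of it. In a simulated random-intercept model with similar SDs (assumed structure, since the report does not state its own), the treatment-by-time SE was 0.0685 with and without subtraction on complete data, and 0.0715 against 0.0713 with the tabled missingness.

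**The case against.** The strongest reply is that the report does not rest on subtraction alone. Table 11 gives raw values by arm and visit, and Table 18 models them. Against raw follow-up, covariate adjustment gains very little: the variance ratios are 1.03, 1.07, 1.01 and 1.04. A reader who uses Table 11 loses almost nothing. This is correct, and it limits the point to the subtracted analysis. It also shows that subtraction is worse than no adjustment at all.

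Change from baseline was also the planned quantity, the estimate is unbiased, and no formal conclusion changes. The only formal thickness claim, the treatment-by-time interaction, is essentially untouched. All of this stands. It makes the point a recommendation and does not invalidate the analysis.

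The unadjusted 95% intervals at 3 and 6 months exclude zero while the Holm p-values do not reach 0.05, so showing them post hoc invites selective reading. That is a real risk, and clear labelling with Holm p-values alongside is needed.

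Finally, the lower end of the range depends on the calculation. With unequal variances, a common slope and the most extreme dropout split at 12 months, the ratio falls to 3.05. The range of 3.2 to 3.9 belongs to the equal-variance calculation, and the conclusion is the same under both.

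**Conclusion.** The concern holds. For bucco-lingual thickness, subtracting the delivery value gives visit-level arm contrasts about 3.2 to 3.9 times the variance of covariate adjustment, and 3.1 to 3.8 times that of the raw follow-up values. This is lost precision and not bias, provided delivery thickness is unaffected by arm, as the report itself argues. Subtraction still carries the chance delivery difference of 0.09 mm into the estimate.

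The size rests on the printed SDs, equal variances, a common slope and, after 1 month, the bounded dropout splits. No visit is below 0.05 after Holm adjustment by either method. What is lost is tighter estimation of a named secondary objective for which no arm difference is currently reported.

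**What to change.** For bucco-lingual thickness only, add a mixed model of the follow-up values with delivery thickness and its interaction with visit as covariates. Report the adjusted arm differences at 1, 3, 6 and 12 months with 95% CIs and Holm-adjusted p-values over the four visits.

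This keeps the planned quantity, because adjusting the change score for delivery thickness gives the same arm difference at each visit. At 3 months, for example, the change-score route gives -0.467 - (0.161 - 1) × 0.095 = -0.387, and the follow-up route gives -0.372 - 0.161 × 0.095 = -0.387.

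Show the result beside the planned change-score results and the Table 18 model, labelled post hoc. Add a version with a separate slope per arm, given the differing 12-month slopes. Canfield and keratinized mucosa width can stay as they are.

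The cost is one extra model on data already collected. The drawback is that the method is chosen after the results are known, so it must not displace the planned analysis.
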